# 13.1.6. Clinical Laboratory Assessments

All blood samples are to be collected following the standard institutional procedures for blood collection and submitted to a central laboratory for analysis.

Instructions on collection, processing, storage and shipping the samples to the central laboratory are located in the Laboratory Manual.

# 13.1.6.1. Hematology

Hematological testing will include complete blood count (CBC) with white blood cell (WBC) differential, hemoglobin, hematocrit, and platelet count

# 13.1.6.2. Serum Chemistry

Serum chemistry testing will include: basic metabolic panel (Glucose, Sodium, Potassium, Chloride, Bicarbonate, BUN, Creatinine, Calcium), comprehensive hepatic panel (Albumin,

Alkaline Phosphatase, Total Protein, ALT, AST, Direct Bilirubin, Total Bilirubin), and Creatine Kinase

#### 13.1.6.3. Cardiac Enzymes

Cardiac enzyme testing will include CK-MB and Troponin I

# **13.2.** Adverse and Serious Adverse Events

#### **13.2.1.** Definition of Adverse Events

#### 13.2.1.1. Adverse Event (AE)

An AE is any untoward medical occurrence associated with the use of a drug in humans, whether or not considered drug related. It may be indicated by physical sign, symptom, clinically significant laboratory abnormalities, and/or disease temporally associated with a medical (investigational) treatment, procedure, or product, whether or not related to the medical (investigational treatment, procedure or product. This definition includes intercurrent illnesses or injuries, exacerbation of pre-existing conditions, or events occurring due to abuse or overdose.

Any condition that was pre-existing is not an adverse event unless there is a change in the nature, severity, or degree of the condition.

Clinical laboratory abnormalities are considered AEs when deemed clinically significant by the Investigator and/or lead to a change in the subject's functional status.

An AE does not include:

- Medical or surgical procedures (e.g., colonoscopy, biopsy). The medical condition that leads to the procedure is an AE.
- Social or convenience hospital admissions where an untoward medical occurrence did not occur.
- Day-to-day fluctuations of pre-existing disease or conditions present or detected at the start of the trial that do not worsen.
- The disease/disorder being studied or expected progression, signs, or symptoms of the disease/disorder being studied unless more severe than expected for the subject's condition.

All Investigators conducting investigative studies supported by Capricor must report both expected and unexpected SAEs to Capricor, or designee, and their individual Institutional Review Board (IRB) in compliance with their institutional policies. Please see Section 13.2.4 or further details on event reporting.

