DMD symptoms begin in early childhood, with degeneration occurring progressively in the skeletal musculature and ultimately in the heart and respiratory muscles, resulting in premature death (Hendriksen et al., 2015). Progressive weakness and muscle atrophy caused by degenerating muscle fibers begins in the lower extremities and pelvis before spreading into the upper extremities. Other symptoms include loss of some reflexes, a waddling gait, frequent falls, difficulty when rising from a sitting or lying position or when climbing stairs, changes to overall posture, and impaired breathing. Many children precipitously lose the ability to run or jump. The atrophied muscles, in particular the calf muscles, and less commonly, muscles in the buttocks, shoulders, and arms, may be enlarged by an accumulation of fat and connective tissue, causing them to look larger and healthier than they actually are ("pseudohypertrophy"). Bone thinning and scoliosis are common. Ultimately, a wheelchair becomes necessary, in most cases between 12 to15 years of age (Henricson et al., 2013).

As the disease progresses, the muscles in the diaphragm that assist in breathing and coughing become weaker. Affected individuals experience breathing difficulties, respiratory infections, and swallowing problems. Almost all DMD patients will develop cardiomyopathy (Aartsma-Rus et al., 2016). Pneumonia, compounded by cardiac involvement, is the most frequent cause of death, which typically occurs in the late teens or early 20s. However, improvements in multidisciplinary care, in particular respiratory care and various forms of assisted ventilation, have extended the life expectancy; numerous individuals with DMD now survive into their 30s, and some even into their 40s (Emery, 2002; Bushby et al., 2010; Bushby et al., 2010).

No pharmacologic or biological therapies proven to stop or reverse the progression of DMD have been approved in the US. Disease management consists primarily of preventive measures as well as active interventions to address the primary and secondary aspects of the disorder.

Page 22 of 75 Capricor, Inc. - Company Confidential

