#### 13.2.1.2. Serious Adverse Event (SAE)

An AE is considered "serious" if, in the view of either the Investigator or Capricor, it results in any of the following outcomes:

- Death
- Life-threatening adverse event

- Inpatient hospitalization or prolongation of existing hospitalization
- Persistent or significant incapacity or substantial disruption of the ability to conduct normal life functions
- Congenital anomaly/birth defect

Important medical events that may not result in death, be life-threatening, or require hospitalization may be considered serious when, based upon appropriate medical judgment, they may jeopardize the subject and may require medical or surgical intervention to prevent one of the outcomes listed in this definition.

Examples of such medical events include bronchospasm requiring intensive treatment in an emergency room or at home, blood dyscrasias, or convulsions that do not result in inpatient hospitalization, or the development of drug dependency or drug abuse.

Complications that occur during a hospitalization are AEs. When the hospitalization is prolonged due to the complication or the complication fulfills any other serious criteria, the event is reported as an SAE. Hospitalization for elective treatment of a pre-existing condition that did not worsen from baseline is not considered an SAE.

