# **15.2.** Clinical Events Committee (CEC)

The purpose of CEC adjudication is to provide consistent and unbiased adjudication of clinical outcomes and specified events through the independent review of source documentation. The charge of the CEC is to review source documents and to adjudicate the classifications of all potential primary safety endpoint events. Sites will be provided instructions in the MOP on how to collect and submit event information required for CEC review. The CEC will remain blinded to subject treatment assignments. The individuals that serve on the committee will be appointed by Capricor, are independent from all other trial activities, and are not affiliated with any investigative site. The committee will consist of, at a minimum, a neurologist and pulmonologist with experience in treating patients with DMD. Additional experts in immunology will be consultants to the committee as necessary. The frequency of CEC meetings is detailed in the CEC Charter.

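### The AE definition does not say whether a hospitalization attributed to expected DMD progression is an SAE, so late, non-fatal respiratory and cardiac admissions may be missed by the SAE primary safety endpoint

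*Protocol*

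**What the plan says.** Protocol section 13.2.1.1 defines an AE and then lists what an AE does not include. One item on that list is "The disease/disorder being studied or expected progression, signs, or symptoms of the disease/disorder being studied unless more severe than expected", with expectation judged against the condition of the subject concerned. The same section points the other way when it describes what counts: "This definition includes intercurrent illnesses or injuries, exacerbation of pre-existing conditions, or events occurring due to abuse or overdose". It adds that a pre-existing condition becomes an AE if its nature, severity or degree changes.

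Protocol section 13.2.1.2 defines an SAE as an AE that, in the view of the investigator or the sponsor, has one of several outcomes. One of these is "Inpatient hospitalization or prolongation of existing hospitalization". Neither section says what happens when an event is both expected progression and serious.

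SAE incidence from baseline through 6 months is a primary safety endpoint (Protocol 7.2.1, SAP 2.2.1). All-cause mortality and acute respiratory decompensation within 2 hours of administration are separate items on the same list. Under Protocol 15.2 the CEC is to "adjudicate the classifications of all potential primary safety endpoint events", working from information that sites submit under instructions in the Manual of Procedures.

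**The concern.** The natural course of DMD runs through the lungs and heart. Protocol section 5.1 says "Affected individuals experience breathing difficulties, respiratory infections, and swallowing problems", and that almost all patients develop cardiomyopathy. The SAP overview describes the parent trial's subjects as having cardiomyopathy secondary to DMD. An investigator can therefore plausibly regard a respiratory or heart-failure admission as expected for a given subject.

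In these organ systems, disease progression and harm from the product can look alike. The trial is open label and has no control arm. If the investigator decides that an admission is progression before anything is entered as an AE, that judgment is not open to review in the way a recorded causality rating is. What is at stake is the completeness of a primary safety endpoint in a trial of at most 10 subjects, where none versus one changes the safety statement.

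**Working it through.** The plan states no event rate, power or precision figure for this endpoint, so there is no figure to reproduce. The main check is to follow an event through the definitions.

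**Path of a non-fatal respiratory or cardiac admission that starts more than 2 hours after infusion**

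1. *Is it an AE?* Under the exclusion in 13.2.1.1 it is not, if it is expected for that subject. Under the exacerbation and change-in-severity sentences of the same section it is. The text does not say which prevails.
2. *Is it an SAE?* Under 13.2.1.2 only an AE can be serious. The sponsor's own view of seriousness also applies only to AEs. If step 1 gives no, hospitalization does not bring the event back.
3. *Is it reported onward?* The 24-hour report to the sponsor and the IRB and DSMB reports in 13.2.4 are triggered by SAEs. Post-infusion examination findings become AEs only if they meet the 13.2.1 definition (13.1.3), which is the same test.
4. *Does the CEC see it?* That depends on what sites submit. SAP 7.1.1 lets the CEC merge events, rename them, or change a reported event to a non-AE. It states no step in the other direction.
5. *Is it in the tables?* SAP 7.1 bases its AE summaries on CEC-adjudicated events. SAP 4.3 counts missing seriousness as serious and missing relatedness as possible, but those rules need a recorded event. Hospitalizations appear by name in the SAP only as prior DMD medical history (5.7).

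Attribution to the disease already has a place. The Unlikely category in Protocol 13.2.2 covers events explained by an alternative cause that is common in the population or the individual.

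**Scale, for illustration only**

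Inputs: n = 10 (Protocol 7.3, an upper limit); event counts are assumed. Incidence = subjects with at least one SAE / n, with exact (Clopper-Pearson) 95% intervals.

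- One subject, whose only SAE is counted: 1/10 = 10%. Lower limit 1 − 0.975^(1/10) = 0.0025; upper limit, the 97.5% point of Beta(2, 9), = 0.445. Interval 0.3 to 44.5%.
- The same event set aside: 0/10 = 0%. Upper limit 1 − 0.025^(1/10) = 0.308. Interval 0 to 30.8%.

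Let p be an assumed 6-month risk of such an admission per subject, and s an assumed share classed as expected progression. The chance of recording at least one is 1 − [1 − p(1 − s)]^10. For p = 10% and s = 0.5 this is 1 − 0.95^10 = 0.401.

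| p | s = 0 | s = 0.5 | s = 1 |
|---|---|---|---|
| 5% | 40% | 22% | 0% |
| 10% | 65% | 40% | 0% |
| 20% | 89% | 65% | 0% |
| 30% | 97% | 80% | 0% |

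Neither p nor s can be taken from the documents.

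**The case against.** The strongest reply is that a sensible reading of the text already captures these events. An unplanned admission for worsening is a change in severity, and a respiratory infection can be an intercurrent illness. The only hospitalizations the protocol expressly sets aside are social or convenience admissions with no untoward occurrence (13.2.1.1) and elective treatment of a condition that has not worsened (13.2.1.2). Eligibility also matters. Section 8.2 excludes LVEF below 35%, near-term risk of respiratory decompensation, serum bicarbonate of 29 mmol/L or more, and acute respiratory illness in the 30 days before screening. For subjects who pass those criteria, a respiratory or heart-failure admission within 6 months would often be more severe than expected, and so an AE. All of this stands. It makes omission less likely, but it leaves two conflicting rules and no statement of which governs.

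The reply also disposes of several stronger readings that a reader might infer:

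- *That the protocol removes progression even when it leads to hospitalization.* No sentence says so; it would be an inference from silence.
- *That such events never reach the CEC.* The submission rules are in the Manual of Procedures, and neither it nor the CEC Charter is among the documents.
- *That nothing is recorded.* Ventilatory support is asked about at Day 1, Month 3 and Month 6 and listed (SAP 5.5). Concomitant medications, pulmonary function and cardiac MRI are listed and summarized (SAP 5.10, 6.2, 6.3), and monitors compare entries with source (Protocol 16.2). These give traces of an event but do not replace an SAE count.
- *That counting deaths separately makes the endpoint set inconsistent.* All-cause mortality is a deliberate separate endpoint and limits the gap.
- *That the related-TEAE endpoint is distorted to the same degree.* An event judged to be progression would probably be rated Unlikely and so not be counted as related.

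**Conclusion.** The point holds as a conflict between definitions with no seriousness override. It concerns mainly non-fatal respiratory or cardiac hospitalizations starting more than 2 hours after infusion that the investigator attributes to expected progression. These may be left out of SAE incidence and may not be adjudicated. Sites can also differ on the same case.

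The size is unknown. With 10 subjects, one affected subject moves incidence by 1/10 = 10 percentage points, but only if that subject has no other SAE; otherwise subject-level incidence does not change. A reader might infer that the reported incidence is biased downward. The documents support only that it could be, since they give no event count and do not show how sites will apply the exclusion. The point is worth correcting because a stated rule could cause the omission, the endpoint is primary, and one sentence resolves it.

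**What to change.** Reconcile Protocol sections 13.2.1.1 and 13.2.1.2 by adding: *The progression exclusion does not apply to any event that meets a seriousness criterion in 13.2.1.2; such events are recorded as SAEs, attribution to DMD is handled in the causality rating (13.2.2), and they are referred to the CEC.* Repeat this in the site instructions.

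Keep the exclusion for non-serious expected progression, such as gradual loss of function. Do not extend the override to every respiratory or cardiac event after the first infusion. That would bring in non-serious decline already measured by the exploratory endpoints, and would defeat the exclusion being kept. The existing exceptions for social admissions and for elective treatment can stay as they are. As an option, the SAP could list all on-study hospitalizations whatever their attribution.

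The cost is protocol wording, site instruction, a few more SAE forms, and a possibly higher SAE count that includes DMD-related events. The causality rating lets the report separate those.

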#### 13.2.1.2. Serious Adverse Event (SAE)

An AE is considered "serious" if, in the view of either the Investigator or Capricor, it results in any of the following outcomes:

- Death
- Life-threatening adverse event

- Inpatient hospitalization or prolongation of existing hospitalization
- Persistent or significant incapacity or substantial disruption of the ability to conduct normal life functions
- Congenital anomaly/birth defect

Important medical events that may not result in death, be life-threatening, or require hospitalization may be considered serious when, based upon appropriate medical judgment, they may jeopardize the subject and may require medical or surgical intervention to prevent one of the outcomes listed in this definition.

Examples of such medical events include bronchospasm requiring intensive treatment in an emergency room or at home, blood dyscrasias, or convulsions that do not result in inpatient hospitalization, or the development of drug dependency or drug abuse.

Complications that occur during a hospitalization are AEs. When the hospitalization is prolonged due to the complication or the complication fulfills any other serious criteria, the event is reported as an SAE. Hospitalization for elective treatment of a pre-existing condition that did not worsen from baseline is not considered an SAE.

#### 13.2.1.3. Expected Adverse Events

As CAP-1002 is comprised of allogeneic cells, immunologic reactions to the product are a possible adverse event. However, to date, no significant immune system adverse events have been identified with any likelihood of relationship to CAP-1002.

There is some risk of developing transient DSA with the CAP-1002 allogeneic product. All subjects will be monitored during the trial for immune sensitization as outlined in Table 3.

Other risks of the infusion procedure include those risks that are possible with the intravenous administration. These include risks related to infection, bleeding, pain, and bruising and/or hematoma at the vascular access site(s).

#### 13.2.1.4. Unexpected Adverse Events

An AE is considered "unexpected" if it is not listed in the Investigator's Brochure or is not listed at the specificity or severity that has been observed, if the Investigator's Brochure is not required or available, or if it is not consistent with the risk information described in the general investigational plan or elsewhere in the current application.

"Unexpected," as used in this definition, also refers to adverse events or suspected adverse reactions that are mentioned in the Investigator's Brochure as occurring with a class of drugs or as anticipated from the pharmacological properties of the drug, but are not specifically mentioned as occurring with the particular drug under investigation.

Expedited reporting is required for serious unexpected AEs as discussed in Section 13.2.4.

#### **13.2.1.5.** Other Adverse Event (OAE)

OAEs will be identified by the Medical Monitor during the evaluation of safety data for the Clinical Study Report. Significant adverse events of particular clinical importance, other than

SAEs and those AEs leading to discontinuation of the subject from the trial, will be classified as OAEs.

For each OAE, a narrative may be written and included in the Clinical Study Report.

#### **13.2.2.** Relationship to Investigational Product

The Investigator will assess the relationship (causality) of an AE to the investigational product and administration procedure.

Causality will be defined as follows:

- *Probable*: adverse events that, after careful medical evaluation, are considered with a high degree of certainty to be related to the investigational product or administration procedure. The following characteristics will apply:
  - A reasonable temporal relationship exists between the event and the investigational product or administration procedure, and
  - The event is a known reaction to the investigational product or administration procedure, which cannot be explained by an alternative etiology commonly occurring in the population/individual.
- **Possible**: adverse events that, after careful medical evaluation, do not meet the criteria for a probable relationship to the investigational product or administration procedure, but for which a connection has reasonable certainty. The following characteristics apply:
  - The event occurs after exposure to the investigational product or administration procedure, and
  - The event is not a known reaction to the investigational product or administration procedure, but cannot be explained by a commonly occurring alternative etiology, or
  - In the absence of a temporal relationship, the event cannot reasonably be explained by an alternative etiology.
- *Unlikely*: adverse events that, after careful medical evaluation, do not meet the criteria for possible or probable relationship to investigational product or administration procedure and for which a connection is unlikely. The following characteristics will apply:
  - The event does not follow a reasonable temporal sequence from administration of the investigational product or administration procedure, or
  - May be explained by commonly occurring alternative etiology in the population/individual, or
  - May have been produced by environmental factors, and there is no apparent pattern of response to the investigational product or administration procedure.

An adverse event will be reported as "related" when causality is evaluated by an Investigator as probably or possibly related to the investigational product and/or the administration procedure.

Related adverse events indicate a potential cause-and-effect relationship between the investigational product and/or administration procedure and the occurrence of the adverse event.

An adverse event will be reported as "unrelated" when causality is evaluated by an Investigator as unlikely related to the investigational product and/or administration procedure by the Investigator. Unrelated adverse events indicate no relationship between the occurrence of the adverse event and the investigational product and/or administration procedure.

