## 7.2. Trial Endpoints

### 7.2.1. Safety Endpoints

The *primary safety endpoints* include the incidence of the following from baseline through the 6-month timepoint:

- Acute respiratory decompensation within 2 hours following IP administration
- Hypersensitivity reaction
  - Hypersensitivity reaction is defined as a clinical syndrome including, but not limited to, fever, leukocytosis, or rash with onset  $\leq 2$  hours post infusion and lasting < 24 hours, in the absence of clinical signs of concomitant infection.
- All-cause mortality
- Serious adverse events

- Treatment-emergent adverse events related to IP or administration procedure
- Immune sensitization syndrome
  - Immune sensitization syndrome shall be defined as: (a) clinical signs and symptoms consistent with systemic inflammation (e.g., fever, leukocytosis, rash, or arthralgia) with onset  $\geq 24$  hours post infusion and the absence of clinical signs of concomitant infection, AND (b) elevation of anti-human leukocyte antigen (HLA) antibodies against the donor cells (i.e., DSAs), detected  $\leq 30$  days following onset of syndrome, of (i)  $\geq 2000$  mean fluorescent intensity (MFI) if baseline MFI  $\leq 1000$ , or (ii)  $\geq 2$  times baseline otherwise

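### Protocol 13.2.2: a well-timed adverse event with a common alternative cause cannot be Probable or Possible, so it is either reported as unrelated or fits no category

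*Protocol*

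**What the plan says.** Protocol 13.2.2 defines three causality categories, each assigned after medical evaluation.

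- **Probable** needs reasonable timing and a known reaction "which cannot be explained by an alternative etiology commonly occurring in the population/individual".
- **Possible** needs exposure first, and then one of two limbs. The main limb is "The event is not a known reaction to the investigational product or administration procedure, but cannot be explained by a commonly occurring alternative etiology". The other is "In the absence of a temporal relationship, the event cannot reasonably be explained by an alternative etiology".
- **Unlikely** is for events that fail the other two "and for which a connection is unlikely". Its listed characteristics are joined by *or*, and one of them is "May be explained by commonly occurring alternative etiology in the population/individual".

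Probable and Possible are reported as related, and Unlikely as unrelated. The section then adds: "Unrelated adverse events indicate no relationship between the occurrence of the adverse event and the investigational product and/or administration procedure".

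One of the primary safety endpoints in Protocol 7.2.1, repeated in SAP 2.2.1, is "Treatment-emergent adverse events related to IP or administration procedure". SAP 7.1 builds its related summaries from TEAEs whose reported relationship is Probable or Possible.

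**The concern.** Causality scales usually keep a middle grade for an event that the product could well have caused but that something else could also explain. Here the middle grade is closed to such events. It is also closed, in its main limb, to recognised reactions.

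Competing explanations will often be available in this population. Protocol 5.1 says of DMD: "Affected individuals experience breathing difficulties, respiratory infections, and swallowing problems". Every subject receives CAP-1002, so there is no concurrent control group against which an under-count of related events would show.

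At stake is the accuracy of one primary safety endpoint. The plan also treats uncertainty unevenly. Under SAP 4.3 an event with a blank relatedness field is counted as Possible, while a timely, recognised reaction with a competing explanation may be counted as unrelated.

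**Working it through.** The plan gives no figure to reproduce on this point: Protocol 14.1 states no formal hypotheses, and no related-event rate appears anywhere. The check is therefore mainly one of logic.

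**Step 1. A well-timed event against the listed characteristics (Protocol 13.2.2).** The environmental-factor characteristic of Unlikely is set aside.

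| Known reaction | Common alternative may explain it | Probable | Possible, main limb | Unlikely characteristic present | Outcome |
|---|---|---|---|---|---|
| yes | no | met | fails (known) | no | Probable |
| no | no | fails (not known) | met | no | Possible |
| no | yes | fails | fails (alternative) | yes | Unlikely, or none |
| yes | yes | fails (alternative) | fails (known, and alternative) | yes | Unlikely, or none |

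The second limb of Possible does not rescue the last two rows. It applies when there is no temporal relationship, and it too requires that no alternative reasonably explains the event.

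**Step 2. Is this an artefact of how the *and/or* in Possible is read?** Take six yes/no attributes: after exposure (A), reasonable timing (T), known reaction (K), common alternative (C), other alternative (O) and environmental factor (E). T requires A, so (A, T) has 3 admissible pairs. With C = yes, the count is 3 × 2 × 2 × 2 (for K, O and E) = 24 combinations. Possible was read both as A and (main limb or second limb), and as (A and main limb) or second limb. Under either reading, 0 of 24 reach Probable or Possible, and all 24 show at least one Unlikely characteristic.

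**Step 3. Add the opening condition of Unlikely.** Step 2 uses only the listed characteristics. Unlikely also requires a judgement that a connection is unlikely. If the investigator makes that judgement, the event is Unlikely and is reported as unrelated. If not, the event fails all three categories.

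**Step 4. Direction.** The related endpoint is Probable plus Possible. The treatment of alternatives only bars events from those two grades and never adds any. Where an investigator resolves a no-fit event by choosing Possible, or leaves the field blank so that SAP 4.3 counts it as Possible, the event stays in. Any misclassification this rule causes is therefore downward.

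**Step 5. Scale, as illustration only.** Protocol 7.3 enrols up to 10. Assume all 10 are infused. Each subject whose only related TEAE is reclassified lowers the incidence by 1/10 = 10 percentage points. The exact 95% limits are the 0.025 quantile of Beta(x, n − x + 1) and the 0.975 quantile of Beta(x + 1, n − x):

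- x = 2, n = 10: 20% (2.5% to 55.6%)
- x = 1, n = 10: 10% (0.3% to 44.5%)

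If a fraction q of subjects with a truly related TEAE is lost, the reported rate is p(1 − q). Both p and q are assumed:

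| True p | q = 10% | q = 25% | q = 50% |
|---|---|---|---|
| 20% | 18% | 15% | 10% |
| 40% | 36% | 30% | 20% |
| 60% | 54% | 45% | 30% |

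**The case against.** The strongest reply is that the scale is applied with judgement. All three grades follow medical evaluation, and Unlikely has its own opening condition. A reader might infer that every event with a common alternative is automatically sent to unrelated. The text does not support that: an investigator who thinks a connection is not unlikely is not directed there. What remains is that this investigator has no grade to use, which is itself a defect in a three-grade scale.

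The plan also has safeguards, each of them partial.

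- **CEC.** It adjudicates potential primary safety endpoints (Protocol 15.2), adjudicated endpoints are described by relatedness (Protocol 14.4.1), and summary tables use adjudicated events (SAP 7.1). But SAP 7.1.1 lists its powers as merging events, changing the term and reclassifying an event as a non-AE. Changing relatedness is not listed, and SAP 7.1 refers to the reported relationship. A non-serious event already called unrelated may never be submitted as a potential endpoint.
- **Visibility.** SAP 7.1 summarises AEs within 24 hours of administration with no stated causality filter, tabulates TEAEs by relationship, and lists all AEs. Unlikely events can be seen, but they are not in the related count.
- **Other endpoints.** Mortality, SAEs, hypersensitivity, acute respiratory decompensation within 2 hours and immune sensitization syndrome do not use this scale.

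Three further inferences go too far. First, a reader might say that any respiratory event after infusion has an alternative by construction. Protocol 5.1 describes DMD in general, and exclusions 3 to 5 in Protocol 8.2 remove subjects at evident near-term respiratory risk. Second, access-site bruising might be offered as an example because blood is also drawn. But sampling may fall on other days (Table 3, footnote 6), the site of the bruise can help separate the causes, and a trial blood draw is not obviously a cause common in the population. Third, one might extend the point to SUSAR reporting. Protocol 13.2.4 does use possible or probable relatedness, but SUSARs must be unexpected, so known reactions are largely outside it. All SAEs go to the sponsor within 24 hours whatever their causality.

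**Conclusion.** The point holds as a defect of definition. On the text of Protocol 13.2.2, a well-timed event that may have a common alternative cause cannot be graded Probable or Possible, and a known reaction is also barred from the main limb of Possible. The event is graded Unlikely and reported as having no relationship, or it has no grade. Any resulting error in the related-TEAE primary safety endpoint is downward.

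A reader might go on to infer that the endpoint is shown to be biased, or driven towards zero. The documents do not support that. They give neither a related-event rate nor the share of events with competing causes, and they do not show how investigators will fill the gap. The figure of 10 percentage points per subject rests on 10 treated subjects and on that subject having no other related TEAE. The intervals for 2/10 and 1/10 overlap almost entirely. The trial is descriptive, so no test or decision threshold is affected.

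**What to change.** Amend Protocol 13.2.2 and the AE form instructions:

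1. In Possible, delete the condition that the event is not a known reaction. Admit events, known or not, with a reasonable temporal relationship and for which the product or procedure is a plausible cause, even though an alternative etiology may also explain them.
2. Limit Unlikely to events with no reasonable temporal relationship, or for which another cause is clearly more likely.
3. Reword the definition of unrelated so that it claims no more than that a connection is unlikely.

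The plausible-cause condition matters. A rule admitting every event to which a contribution cannot be excluded would be too broad and could make most timely events Possible.

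The cost is a wording change. The downside is that the reported related-TEAE rate may be somewhat higher and slightly less specific.
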